**Table 3 Intercurrent Events Impacting Primary Analysis**

Intercurrent Event	SDCR/NSDCR	Estimand Approach
Withdrawal from study treatment due to lack of efficacy	SDCR	Treatment Policy
Withdrawal from study treatment due to safety or tolerability reason (NOTE: This will include discontinuation due to AE, incl. suspected or confirmed COVID-19 AEs)	SDCR	Treatment Policy
Withdrawal from study treatment with no informative reason given	SDCR	Treatment Policy
Withdrawal from study treatment due to the COVID-19 pandemic	NSDCR	Hypothetical Strategy
Substantial reduction in drug exposure due to the COVID-19 pandemic (defined as $\geq 4$ missed dose-months)	NSDCR	Hypothetical Strategy
Withdrawal from study treatment due to purely administrative reason	NSDCR	Hypothetical Strategy
Death	NSDCR	Hypothetical Strategy
Withdrawal from study treatment due to use or initiation of protocol prohibited medication	SDCR	Treatment Policy
Withdrawal from study treatment due to other SDCR ICEs	SDCR	Treatment Policy

AE = adverse event; COVID-19 = coronavirus disease 2019; NSDCR = Non Study Drug or Condition Related; SDCR = Study Drug or Condition Related

### ICE Derivation

Identification and categorization of the ICEs will be done based on fully blinded data only and will be finalized before database lock.

The number of missed dose-months due to the COVID-19 pandemic will be derived from the standardized eCRF data fields. More specifically, any Q4W missed dose due to COVID will count as 1 missed dose-months, while any Q2W missed dose due to COVID will count as 0.5 missed dose-months. The information whether a dose was missed due to COVID will be derived from the corresponding “reason for missed visit” and “reason for missed dose” fields in the eCRF.

All occurrences of “withdrawal from study treatment” ICE, as per [Table 3](#), will be identified and categorized as SDCR/NSDCR based on the standardized reason reported in the eCRF “Study Drug Completion/Early Discontinuation” form. In case of ambiguity (i.e., if the reason for study drug discontinuation as reported in the eCRF is either “Protocol deviation”, “Withdrawal by subject”, “Physician decision” or “Other”), an adjudication committee will review the dedicated eCRF free text field and assign the withdrawal to a pre-specified ICE and a corresponding SDCR or NSDCR category. The

adjudication committee may also introduce additional ICES to the list, in case where no appropriate fit is found in [Table 3](#) or [Appendix 2](#) . The adjudication committee members must not have been involved in the conduct of Studies GRADUATE I and GRADUATE II and must not have been exposed to unblinding data from these studies. The members of the adjudication committee must have signed the charter of the adjudication committee, in [Appendix 3](#).

### 5.3.3 Main Analytical Approach for Primary Estimand and Primary Endpoint

#### Primary study hypothesis

The primary efficacy analysis for this study will test the superiority of the active drug over the placebo at Week 116 with a two-sided test corresponding to the following null hypothesis,  $H_0$ , and alternative hypothesis,  $H_1$ :

$$H_0: \mu_{\text{active}} = \mu_{\text{placebo}}$$

$$H_1: \mu_{\text{active}} \neq \mu_{\text{placebo}}$$

Where  $\mu_{\text{active}}$  and  $\mu_{\text{placebo}}$  are the mean changes from baseline to Week 116 in the CDR-SB score for each arm.

#### Time Windowing

For the primary endpoint (and in general for clinical efficacy endpoints) the following time windows will be used for analyses (see [Table 4](#)), based on study days. Study days are defined based on days on study since the date of the first dose, with the day of the first dose being study day 1.

**Table 4 Time windows for clinical endpoint assessments**

Visit	Target day	Time window (in study days*)
Baseline	1	Up to Day 35
Week 24	169	72, 266
Week 52	365	267, 448
Week 76	533	449, 630
Week 104	729	631, 770
Week 116	813	771, earliest between 897 or first dose of OLE

In cases where more than one assessment falls within a time window, the assessment with the date closest to the target day is selected whether it's a scheduled, unscheduled or an early termination visit.

With regards to an ICE of withdrawal from study treatment, an assessment will be regarded as having happened after the ICE of withdrawal from study treatment if it is collected >28 days since the last dose.

### **General strategy to address the ICEs**

For the primary estimand, a treatment policy approach will be used for all SDCR ICEs. In line with the clinical question of interest, the aim is to estimate a treatment effect irrespective of the occurrence of these ICEs. This approach is largely in line with the EMA guideline on the clinical investigation of medicines for the treatment of AD ([EMA 2018](#)).

All NSDCR ICEs will be handled using a hypothetical approach. The aim is to estimate a treatment effect “as if” the ICE had not happened. Post-ICE outcome values compatible with a hypothetical strategy are not directly observable. Consequently, any observed outcome values after NSDCR ICEs will be removed and treated as missing data for analysis purposes.

For participants with multiple ICEs, the type of the first ICE will determine the strategy to be considered.

### **Missing data assumptions for the primary estimator**

For intermittent missing data (i.e., for participants with non-missing Week 116 data but missing data at other visits), missing data not associated with an ICE (e.g., for participants who had completed Week 104 visit before protocol v4 was implemented), and for missing data after NSDCR ICEs (handled with a hypothetical strategy), the missing data are assumed to be similar to those from the other participants in the same treatment group with no such missing data. This is compatible with a missing-at-random (MAR) assumption.

All observed data after SDCR ICEs will be included in the analysis. If data after SDCR ICEs are missing, they will be assumed to be similar to those in the placebo group for both study arms. Specifically, data will be imputed based on the placebo arm using reference based imputation with a Copy Increments from Reference (CIR) assumption ([Carpenter et al, 2013](#) and [Cro et al, 2020](#)). This approach appears conservative yet plausible for the study drug. CIR assumes that changes in the primary endpoint after the ICE in a participant randomized to active drug can be represented by, i.e., imputed from, that of participants randomized to placebo. It therefore assumes no treatment effect after the ICE. In the placebo arm, this is compatible with a MAR assumption whereas in the active drug arm, the imputation is under a Missing Not At Random (MNAR) assumption.

Further details about the implementation of the missing data imputation are provided below. Sensitivity analyses for the missing data assumptions are discussed in Section [5.3.4](#).

### **Description of the primary estimator**

The primary estimator will be applied to the ITT analysis set (see [Table 2](#)) and it will be implemented using four steps. First, an imputation model will be fitted to the data. Second, imputation of missing data will be performed based on the parameter estimates from the imputation model. Third, the completed data will be analyzed using an analysis of covariance (ANCOVA) model. Finally, inference will be performed based on resampling techniques. All four steps are described and justified in a published manuscript ([Wolbers et al. 2022](#)) which provides a more detailed justification of the statistical methodology and supportive simulations. Considerations about the control of type-I error for the primary estimator and supportive simulations, mimicking the setting of the GRADUATE I and GRADUATE II studies and exploring an extended range of plausible scenarios for missing data, are provided in the [Appendix 1](#).

#### *1. Imputation model*

The imputation model is a mixed effects model for repeated measures (MMRM) with the longitudinally assessed change from baseline in CDR-SB as the dependent variable. Its purpose is to estimate mean trajectories and covariance matrices of longitudinal outcomes in the placebo and active drug arms, respectively, while subjects remain on their randomized treatment. Therefore, all data after withdrawal from study treatment will be removed and considered as missing for the purpose of estimating the imputation model, and for this purpose only. If these data were not excluded, then the imputation model would estimate mean trajectories based on a mixture of observed pre- and post-discontinuation data. These would not be compatible with the CIR assumption employed in the subsequent imputation step, which requires combining mean trajectories while on active drug up to the ICE with increments while on placebo thereafter, respectively.

The imputation model includes the following covariates: treatment group, visit, and treatment-by-visit interaction, baseline CDR-SB score and baseline CDR-SB score-by-visit interaction, baseline ADAS-Cog 13 total score, baseline ADCS-ADL total score and the randomization stratification factors, namely: disease stage (from the eCRF), geographic region (from the IxRS), the use of AD medication at baseline (derived from the eCRF based on a search of medications; see below for more details) and the APOE  $\epsilon$ 4 status (from the Vendor). For geographic region, IxRS is preferred over the eCRF source, to keep the “starting” region for analysis, in case a participant moved to a different region during the study (the eCRF would otherwise reflect the “final” region). AD medication at baseline will be defined as any use of donepezil, galantamine, memantine or rivastigmine prior to randomization and with an

end date not before the randomization date. An unstructured variance-covariance structure will be applied to model the within-subject errors across visits. If the model fails to converge, then a heterogeneous Toeplitz covariance structure will be used instead and if this still fails, then a compound symmetry covariance structure will be used.

Imputations will be based on restricted maximum likelihood (REML) estimation of the regression and covariance parameters from the imputation model ([von Hippel and Bartlett 2021](#); [Wang and Robins 1998](#)).

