#### **1.2.1 Treatment Assignment and Blinding**

Randomization will be performed centrally using an interactive voice or Web-based response system (IxRS). After screening, participants who meet all eligibility criteria will be randomly assigned to one of two treatment groups (active drug or placebo). The ratio will be 1:1; one active to one placebo. The randomization method will be stratified block-randomization. Randomization to treatment allocation will be stratified by geographic region (Western Europe and Australia vs. Rest of the World vs. North America), participant APOE  $\epsilon$ 4 status (carrier vs. non-carrier), participant stage of disease (prodromal vs. mild AD), use of AD medication (presence vs. absence), and participation in the longitudinal amyloid and tau PET substudies. Except in circumstances in which a Health Authority, Ethics Committee, or Institutional Review Board requires it, a participant will not be told of his or her APOE  $\epsilon$ 4 status. Individual participant APOE  $\epsilon$ 4 genotype results will be blinded to participants, Investigators, and the Sponsor. APOE  $\epsilon$ 4 status information will be supplied directly to the IxRS vendor by the central testing laboratory so that the information can be incorporated at the time of randomization. For participants for whom APOE  $\epsilon$ 4 status is already known, the results will be blinded to the Sponsor and, as much as possible, to the site and central MRI reader.

The study is to be conducted in a double-blind manner to minimize potential bias from Investigators and participants. The Sponsor will be blinded to study treatment. In the OLE phase, the Sponsor, participants, and site staff will remain blinded to previous treatment allocation.

The randomization method implemented in the China extension cohort will be the same as that implemented in the global population.

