## *3. Analysis step*

The completed data (using conditional mean imputation as described above) will be analyzed using an ANCOVA model with the change from baseline in CDR-SB at the Week 116 visit as the dependent variable. This analysis model includes treatment group as the primary covariate with adjustment for the same set of covariates as for the imputation model described above, namely baseline CDR-SB score, baseline ADAS-Cog 13 total score, baseline ADCS-ADL total score and the randomization stratification factors namely: disease stage (from eCRF), geographic region (from the IxRS), the use of AD medication at baseline (derived from eCRF based on a search of medications; see below for more details) and the APOE  $\epsilon$ 4 status (from the Vendor). For geographic region, IxRS is preferred over the eCRF source, to keep the "starting" region for analysis, in case a participant moved to a different region during the study (the eCRF would otherwise reflect the "final" region). AD medication at baseline will be defined as any use of donepezil, galantamine, memantine or rivastigmine prior to randomization and with an end date not before the randomization date. The primary treatment effect estimator is defined as the regression coefficient associated with the treatment group. The treatment effect will be reported as a difference in adjusted means. The treatment

effect at the other visits will be estimated in the same way and will be reported as supplementary analyses of the primary endpoint (see Section 5.3.5).

Percent relative difference, defined as 100 times the estimated treatment effect divided by *the absolute value of the* placebo arm estimate, will also be reported, for all visits, as a point estimate for descriptive purposes. Importantly, ANCOVA is applied to a complete dataset after appropriate missing data imputation. For complete data, ANCOVA applied to outcomes from a single visit is equivalent to a more complex MMRM model. It can be demonstrated that it leads to identical parameter estimates as a corresponding MMRM model with an arbitrary covariance structure if separate regression coefficients are estimated at different visits for all covariates (Amemiya 1985, p. 197).

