#### 4. Inference step

Inference will be based on resampling techniques as recommended by von Hippel and Bartlett 2021. Specifically, the jackknife (Efron and Tibshirani, 1994) will be used to estimate the standard error of the primary treatment effect estimator and the test of the primary statistical hypothesis will be based on the corresponding Z-score. Compared to other resampling techniques, the jackknife has the advantage of providing a deterministic standard error estimate and, hence, removing any simulation randomness from the procedure.

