### **MMRM**

This analysis aims to provide a reference point analysis method described in early versions of the protocol (up to version 4) and to other external analyses where MMRM was considered the default and primary analysis. All available data will be used in the analysis. There will be no missing data imputation or consideration for any intercurrent events. The model will include the following covariates: treatment group, visit, and treatment-by-visit interaction, baseline CDR-SB score and baseline CDR-SB score-by-visit interaction, baseline ADAS-Cog 13 total score, baseline ADCS-ADL total score and the randomization stratification factors, namely: disease stage (from eCRF), geographic region (from the IxRS), the use of AD medication at baseline (from eCRF) and the APOE ε4 status (from the Vendor). An unstructured variance-covariance structure will be applied to model the within-subject errors across visits. In the case of non-convergence, compound symmetry will be used, together with a robust estimator of standard error (“sandwich” estimator).

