#### **5.4 SECONDARY ENDPOINTS ANALYSES**

The same primary estimand's analysis strategy (see Section 5.3.2) will be applied to secondary endpoints listed in Table 5, with the following exceptions for the corresponding estimator:

- *. the imputation model will not include, as covariates, the baseline ADAS-Cog 13 total score and the baseline ADCS-ADL total score*

*The imputation model will thus include treatment group, visit, and treatment-by-visit interaction, the baseline score and the baseline score-by-visit interaction, and the randomization stratification factors, namely: disease stage, geographic region, the use of AD medication at baseline and the APOE ε4 status*

- *the analysis model will not include, as covariates, the baseline ADAS-Cog 13 total score and the baseline ADCS-ADL total score*

*The analysis model will thus include treatment, the baseline score and the randomization stratification factors, namely: disease stage, geographic region, the use of AD medication at baseline and the APOE ε4 status*

In the following, confirmatory secondary endpoints refer to endpoints included in the type I error control procedure. Other important secondary endpoints not subject to the type I error control procedure are considered as supportive secondary endpoints. For all secondary endpoints, the treatment effect over time will also be considered and the change from baseline to Weeks 24, 52, 76, and 104 will be provided as supplementary analyses.

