## **5.7 OTHER ANALYSES**

### **5.7.1 Summaries of Conduct of Study**

The summary of study conduct will include a description of the following items by treatment arm:

- Number of participants enrolled and randomized
- Number of participants included in each analysis set
- Number and percentage of participants who prematurely withdrew from the study or from study treatment (including the reasons for discontinuation and the distribution of these discontinuations by time-windowed visit)
- Incidence of protocol deviations – overall and by four main categories (inclusion criteria, exclusion criteria, medication and procedural)
- Stratification factor reported in IxRS and used for randomization
- Number of participants with home nursing
- Number of participants initiating or changing symptomatic treatment of AD during the study

Major protocol deviations and premature withdrawals will be listed.

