### **5.7.7 Cerebrospinal Fluid (CSF) Analyses**

The main analysis for the CSF biomarkers will be based on the pooled dataset of GRADUATE I and GRADUATE II studies (due to the small number of CSF samples within each study). Analyses at individual study level will be conducted as well.

Analysis of CSF biomarkers will be based on the CSF-mITT analysis set unless otherwise specified.

CSF biomarker data will be summarized by treatment group and visit (see schedule of assessment in the study protocol).

*For each CSF biomarker, two statistically equivalent ANCOVA models will be considered:*

- 1. using the change from baseline to Week 116 as dependent variable, with covariates: treatment arm (as categorical), APOE ε4 status (as categorical; carrier vs non-carrier) and baseline biomarker.*
- 2. using the value at Week 116 as the dependent variable, with covariates: treatment arm (as categorical), APOE ε4 status (as categorical; carrier vs non-carrier) and baseline biomarker.*

Both models will use log (base 10) transformed biomarker data. The following summary statistics will be estimated after the appropriate back-transformation of the original model parameters:

- The geometric mean at Week 116 for each treatment arm, obtained as  $10^{\text{LSM}}$ , where LSM is the least square mean for the corresponding treatment arm based on model 2.
- The geometric mean ratio (gantenerumab relative to placebo) at week 116, obtained as  $10^{\text{LSM\_GvsP}}$ , where LSM\_GvsP is the least square means of the contrast of Gantenerumab against placebo based on model 2.
- The %-difference in geometric mean (relative to placebo) at week 116, obtained as  $[(10^{\text{LSM\_GvsP}}) - 1] * 100$  based on model 2.

- *The %-change from Baseline to Week 116 in the Geometric Mean for each treatment arm, obtained as  $[10^{LSM} - 1] * 100$ , where LSM is the least square mean for the corresponding treatment arm at the corresponding visit based on model 1*

There will be no data imputation for missing data.

The following CSF biomarkers will be analyzed:

- Total tau (tTau)
- Phosphorylated tau (pTau-181)
- Neurogranin
- Neurofilament light (NFL)

Other exploratory CSF biomarker may be reported separately.

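### Randomisation uses five stratification factors, but the efficacy models adjust for four and leave out PET-substudy participation; the pooled CSF model also has no study term.

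*SAP*

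**What the plan says.** **Randomisation.** SAP 1.2 and 1.2.1 and protocol 4.2 describe stratified block randomisation by geographic region, APOE ε4 status and disease stage, and then by "use of AD medication (presence vs. absence), and participation in the longitudinal amyloid and tau PET substudies". That is five factors.

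**Efficacy models.** In SAP 5.3.3 the imputation model adjusts for "the randomization stratification factors, namely: disease stage (from the eCRF), geographic region (from the IxRS), the use of AD medication at baseline" and APOE ε4 status, and the ANCOVA for "the randomization stratification factors namely: disease stage (from eCRF), geographic region (from the IxRS), the use of AD medication at baseline" and APOE ε4 status. The supplementary MMRM in SAP 5.3.5.2 has the same list. For the secondary endpoints (SAP 5.4) the models include "the randomization stratification factors, namely: disease stage, geographic region, the use of AD medication at baseline" and APOE ε4 status, and SAP 5.5 repeats this for the exploratory endpoints. SAP 5.4.1 carries the list into the MMRMs for the confirmatory secondary endpoints by cross-reference. PET-substudy participation appears in none of them, and no reason is given.

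**Inference.** The jackknife "will be used to estimate the standard error of the primary treatment effect estimator" (SAP 5.3.3, inference step).

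**Data held.** SAP 5.7.1 will tabulate by arm the "Stratification factor reported in IxRS and used for randomization".

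**CSF.** SAP 5.7.7 states: "The main analysis for the CSF biomarkers will be based on the pooled dataset of GRADUATE I and GRADUATE II studies". The covariates are treatment, APOE ε4 status and the baseline biomarker. The pooled tau PET model in SAP 5.7.6.3 also has study and study-by-visit terms.

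**The concern.** The SAP presents its covariate list as the complete set of factors used to randomise, and it is not. A reader of the study report would take the analysis to reflect the whole randomisation scheme when it reflects four fifths of it.

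There is also a small statistical cost. Blocking within strata makes the arms more alike on PET participation than chance would. If that factor predicts decline, the treatment estimate varies less from trial to trial than it would under simple randomisation. A delete-one jackknife treats participants as independent units, so it reflects that gain only if the factor is in the model. Without it, the standard error is a little too large and the test slightly conservative.

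The CSF point is similar. Treatment was randomised within each trial, so study should be close to balanced across arms. A difference in level between the trials that remains after adjustment for baseline then adds residual variance that a study term would remove. The SAP pools CSF because each study has few samples, so precision matters there.

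**Working it through.** **1. Reproduce the plan's sample size (SAP 3).** Inputs: placebo change 2.5, effect 30% of that (0.75 points), SD 2.97, two-sided α 0.05, power 90%, allowance 35%.

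- n per arm = 2 × (1.960 + 1.282)² × 2.97² / 0.75² = 329.5, so 330.
- 330 / 0.65 = 507.7, so 508 per arm and 1016 in total. This matches the plan.
- Effective number: 1016 × 0.65 = 660.4. SE = 2.97 × √(4/660.4) = 0.231. Power = Φ(0.75/0.231 − 1.96) = 90.06%.

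This is an unadjusted t-test calculation, so adding a covariate does not change 1016.

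**2. Compare the lists.**

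| Factor | Randomisation | Efficacy models |
|---|---|---|
| Disease stage | yes | yes (eCRF) |
| APOE ε4 | yes | yes (vendor) |
| AD medication | yes | yes (eCRF) |
| Region | yes | yes (IxRS) |
| PET-substudy participation | yes | **no** |

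The sources shown are those given for the primary model.

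**3. Size of the PET omission.** Let R² be the share of residual variance explained by PET participation. The documents give no value, so 0.5%, 1% and 2% are assumed; at 0% the cost is nil. If blocking balances the factor, the true SD of the estimate is SE × √(1 − R²). The model without the factor reports SE; the model with it reports SE × √(1 − R²).

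- Overstatement of the SE = 1/√(1 − R²) − 1
- Type I error without the factor = 2 × [1 − Φ(1.96/√(1 − R²))]
- Power without = Φ[(0.75/SE − 1.96)/√(1 − R²)]
- Power with = Φ[0.75/(SE × √(1 − R²)) − 1.96]

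| R² (assumed) | SE too large by | Type I error without | Power without | Power with |
|---|---|---|---|---|
| 0.5% | 0.25% | 4.94% | 90.11% | 90.20% |
| 1% | 0.50% | 4.89% | 90.17% | 90.34% |
| 2% | 1.02% | 4.77% | 90.28% | 90.62% |

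The like-for-like power cost is 0.1, 0.2 and 0.3 points. Against the plan's 90.06% the gain would read as 0.1 to 0.6 points, but that also counts the benefit of stratified randomisation itself.

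**4. Simulation check.** Assumed: 48 strata (3 × 2 × 2 × 2 × 2), blocks of 4, 20% of participants in the PET substudies, complete data.

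- With 660 participants, the delete-one jackknife and 20,000 trials per case: at R² 2% the mean SE was 0.2322 without the factor and 0.2301 with it, type I error 4.83% against 4.96%, and power 90.3% against 90.5%. At R² 1%, type I error was 4.91% against 4.96% and power 90.2% against 90.3%.
- With 1016 participants, a model-based SE and 4,000 trials per setting (Monte Carlo error √(0.05 × 0.95/4000) ≈ 0.3 points): at R² 0%, 1%, 5% and 10%, type I error was 5.0%, 4.6%, 4.5% and 3.9% without the factor, and 5.0%, 4.9%, 5.0% and 4.7% with it. The estimate was unbiased either way.

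**5. CSF.** The same overstatement formula, with an assumed share of 0.5%, 2% or 5% explained by study after the baseline biomarker, gives 0.25%, 1.0% and 2.6%. In a simulation with 100 participants per study and a between-study shift of 0 to 0.5 SD (both assumed), type I error was 4.5% to 4.8% without a study term and 4.7% to 4.9% with one.

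**The case against.** - **The planned power is met anyway.** This is true: power without the PET factor is still 90.11% to 90.28% in the table. The type I errors of 4.77% to 4.94% also lie inside the 4.69% to 5.18% that SAP Appendix 1 accepts as consistent with control. However, Appendix 1 describes 1:1 allocation without strata, so it does not address this point.
- **Nothing shows that PET participation is prognostic.** Also true. What counts is the variance left after baseline CDR-SB, ADAS-Cog 13, ADCS-ADL and the four listed factors, and that may be close to zero. The simulations use complete data and do not run the imputation estimator. This limits the size of the point; it does not remove the mismatch.
- **The models are unambiguous, and the SAP does not copy the IxRS values for the other factors either.** The same four covariates are named each time, so no choice is left to the analyst. But the other four factors are at least represented, from whichever source. The PET factor is absent, and the list is still labelled as the randomisation factors.
- **Adding a covariate is more than wording.** It changes the primary model for both trials at SAP version 3, after an advanced version went to the FDA. This stands as a procedural cost.
- **CSF is a lesser matter.** It is a pharmacodynamic biomarker outside the testing hierarchy, the trials are identical in design, and analyses by individual study are planned. Tau PET is a single substudy with a repeated-measures model, so the two models need not match in every term. All of this lowers the weight of the CSF point, but the pooled CSF analysis is the main one and no reason is given for leaving study out.

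**Conclusion.** The concern holds in both parts. It is a specification mismatch with a small precision cost and does not threaten validity: the estimate is unbiased and type I error is not inflated. With PET participation explaining 0.5% to 2% of residual variance, the omission overstates the standard error by 0.25% to 1.02% and costs 0.1 to 0.3 points of power. For pooled CSF, a study share of 0.5% to 5% overstates the standard error by 0.25% to 2.6%. All these shares are assumptions; if the true shares are zero, nothing is lost. The count of five factors against four, and the missing study term, rest on no assumption. The change is worth making because it recovers whatever precision is available and brings the analysis into line with the way participants were randomised.

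**What to change.** Before unblinding:

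1. Add PET-substudy participation, as coded in the IxRS, to the imputation and ANCOVA models for the primary, secondary and exploratory endpoints and to the MMRMs (SAP 5.3.3, 5.3.5.2, 5.4, 5.4.1, 5.5). State its levels, since the documents name amyloid and tau participation together as one factor.
2. If the sponsor has a reason to leave it out, state the reason and stop describing the four covariates as the stratification factors. This corrects the label but recovers no precision.
3. Add study as a covariate in both pooled CSF ANCOVA models (SAP 5.7.7).

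**Cost.** A SAP amendment for both trials, one or a few degrees of freedom, and no new data, because the IxRS strata are already to be summarised. If the imputation model then fails to converge, SAP 5.3.6 already provides for dropping covariates or pooling levels. Sample size is unaffected.
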